#### TSQM

TSQM-14 is an instrument to assess patient's satisfaction with medication, providing scores on 4 scales: side effects, effectiveness, convenience and global satisfaction. With the exception of item (i.e., question) 4 (presence of side effects; yes or no), all items have 5 or 7 responses, scored

from 1 (least satisfied) to 5 or 7 (most satisfied). Higher scores indicate higher satisfaction. Scores for each domain are computed by adding the TSQM items in each domain and then transforming the composite score into a value ranging from 0 to 100. Of note, a score can be computed for a domain only if no more than one item is missing from that domain. The calculations specific to each domain are presented in detail below.

Global Satisfaction([(Sum (Item 12 to Item 14)) – 3] divided by 14) \* 100 If Item 12 or 13 is missing: ([(Sum (the 2 completed items)) – 2] divided by 10) \* 100 If Item 14 is missing: ([(Sum (Item 12 and Item 13)) – 2] divided by 8) \* 100

*Effectiveness* ([(Item 1 + Item 2 + Item 3) – 3] divided by 18) \* 100 If one item is missing: ([Sum (the 2 completed items)) – 2] divided by 12) \* 100

Side Effects If Question 4 is answered 'No' then score = 100Else ([Sum (Item 5 to Item 8) – 4] divided by 16) \* 100 If one item is missing: ([(Sum (the 3 completed items)) – 3] divided by 12) \* 100

Convenience ([Sum (Item 9 to Item 11) – 3] divided by 18) \* 100. If one item is missing: ([(Sum (the 2 completed items)) – 2] divided by 12) \* 100

The 14 items are listed in the Appendices.

Each derived score will be summarized descriptively as a continuous variable.

## SF-36

SF-36 is a self-administered, generic health status questionnaire consisting of 36 questions that measure 8 health concepts: physical functioning, role limitations due to physical problems, bodily pain, general health perception, vitality, social functioning, role limitations due to emotional problems and mental health (MH).

The SF-36 has a single item covering change in health status over the last year and 8 multi-item scales. Two summary scales (Physical and Mental) have also been derived using factor analytic methods. Scales are set up so that a higher score indicates better health.

The SF-36 questionnaire is reported in the Appendices.

The reference tool for the derivation of the composite scores will be the scoring software provided by Optum, PRO CoRE: SF-36v2.

The algorithm used by this software has 5 steps for the scoring of the profile scales:

- 1. Data Cleaning and Item Recoding
- 2. Item Recalibration
- 3. Computation of Raw Scores
- 4. Transformation of Raw Scale Scores to 0-100 Scores
- 5. Transformation of 0-100 Scores to T-score Based Scores

After these steps, the component summary measures are derived as follows:

- 1. Standardization of the SF-36v2® Health Survey Scales
- 2. Aggregation of the Scale Scores
- 3. Transformation of Summary Scores

Details for the above steps are included in the manual provided with the software.

Missing item can be replaced using Maximum Data Recovery (Max). With this method the software applies a value to a scale item rendered missing if at least one of the items in that scale has valid data. A scale receives a "missing" score (".") only if all the items in that scale are missing. Physical Components Summary Score (PCS) and Mental Component Summary Score (MCS) are calculated when at least 7 of the 8 profile scales have valid data, either actual or estimated.

However, to calculate PCS, the Physical Function (PF) scale must be one of the 7 scales having valid data. Also, to calculate MCS, the MH scale must be one of the 7 scales having valid data.

#### MFIS-5

MFIS-5 is a modified form of the Fatigue Impact Scale that consists of 5 questions that assess the impact of fatigue on physical, cognitive, and psychosocial functioning, with 5 response levels ranging from 0 ("Never") to 4 ("Almost always"). Total scores range from 0 to 20, with higher scores representing a greater impact of fatigue.

Consider the following scale: 0 (Never), 1 (Rarely), 2 (Sometimes), 3 (Often), 4 (Almost always).

The following items from the MFIS constitute the MFIS-5:

- I have been less alert
- I have been limited in my ability to do things away from home
- I have had trouble maintaining the physical effort for long periods
- I have been less able to complete tasks that require physical effort
- I have had trouble concentrating.

Each item (and the total score) will be summarized descriptively considering the raw scores as values of a continuous variable.

No imputation will be performed if any items in the MFIS-5 are missing.

#### **BDI-FS**

The 7 items BDI-FS is a self-report inventory for measuring the severity of depression on a 7-item scale. The BDI-Fast Screen is scored by summing all of the highest ratings for each of the 7 items. Each item is rated on a 4-point scale ranging from 0 to 3. The maximum total score is 21. Higher scores indicate greater symptom severity. If an examine has multiple endorsements for an item, then the statement with the highest rating should be scored.

The 7 items are the following: Sadness, Pessimism, Past Failure, Loss of Pleasure, Self-Dislike, Self-Criticalness, Suicidal Thoughts.

Each item (and the total score) will be summarized descriptively considering the raw scores as values of a continuous variable.

No imputation will be performed if any items in the BDI-FS are missing.

#### WPAI-MS

The WPAI-MS questionnaire is a 6-items validated instrument to measure impairments in work and activities. The WPAI yields 4 types of scores: 1. Absenteeism (work time missed); 2. Presenteeism (impairment at work/reduced on-the-job effectiveness); 3. Work productivity loss (overall work impairment/absenteeism plus presenteeism); 4. Activity Impairment. WPAI outcomes are expressed as impairment percentages, with higher numbers indicating greater impairment and less productivity.

WPAI outcomes are expressed as impairment percentages, with higher numbers indicating greater impairment and less productivity, i.e., worse outcomes, as follows:

Questions:

1 = Are you currently employed (working for pay)?

2 = During the past 7 days, how many hours did you miss from work because of problems associated with your multiple sclerosis (MS)?

3 = During the past 7 days, how many hours did you miss from work because of any other reason, such as vacation, holidays, time off to participate in this study?

4 = During the past 7 days, how many hours did you actually work?

5 = During the past 7 days, how much did your MS affect your productivity while you were working? (Scale 0-10)

6 = During the past 7 days, how much did your MS affect your ability to do your regular daily activities, other than work at a job? (Scale 0-10)

Scores:

Multiply scores by 100 to express in percentages.

- 1. Percent work time missed due to health: Q2/(Q2+Q4)
- 2. Percent impairment while working due to health: Q5/10

- 3. Percent overall work impairment due to health: Q2/(Q2+Q4)+[(1-(Q2/(Q2+Q4)))x(Q5/10)]
- 4. Percent activity impairment due to health: Q6/10

Each score (percentage) will be summarized descriptively as a continuous variable.

No imputation will be performed if any items in the WPAI-MS are missing.

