#### Handling of missing data

Unless otherwise specified, missing data will not be replaced.

Missing statistics, e.g. when they cannot be calculated, should be presented as "nd". For example, if n=1, the measure of variability SD cannot be computed and should be presented as "nd".

Where tables are presented over time, the total of missing and non-missing observations at each timepoint should reflect the population still in the study at that time. For example, if a patient is still in the study at the timepoint but with missing data, it should be counted in the number of missing observations.

For PRO items with missing responses, the response will be managed as described in sections 16.3 and 16.4.

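### The WPAI-MS scoring in SAP 16.3 leaves overall work impairment missing for a patient off work all week because of MS who leaves Q5 blank, although the formula fixes it at 100%, and it does not separate patients not employed from non-responders.

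*SAP*

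**What the plan says.** SAP section 16.3 (WPAI-MS) lists six items and four scores. Write A = Q2/(Q2+Q4), where Q2 is hours missed because of MS and Q4 is hours worked, both over the past 7 days.

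- Score 1, absenteeism: A
- Score 2, presenteeism: Q5/10
- Score 3, overall work impairment: A + (1 − A) × Q5/10
- Score 4, activity impairment: Q6/10

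Q5 asks: "During the past 7 days, how much did your MS affect your productivity while you were working". The only missing-item rule is: "No imputation will be performed if any items in the WPAI-MS are missing". Q1 asks about current paid employment, but it enters no score, denominator or summary.

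SAP section 9 (Handling of missing data) sends missing PRO items to section 16.3 and adds that "if a patient is still in the study at the timepoint but with missing data, it should be counted in the number of missing observations". WPAI-MS is a secondary PRO. It is summarised descriptively at baseline and as change at Months 6, 12 and 24.

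**The concern.** Two situations that the questionnaire is bound to meet have no rule.

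The first is the employed patient who worked no hours in the week because of MS. Q5 does not apply to that patient, so a blank is the natural response. Score 3 contains Q5, and a literal evaluation with Q5 missing returns missing, even though Q5 is multiplied by zero. The value lost is the maximum of the scale, so the loss is selective.

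The second is the patient who is not employed. Scores 1 to 3 have no meaning for that patient. Under section 9 the patient is counted as missing, in the same cell as someone who did not complete the form. A reader of the tables could not tell leaving work from non-response, although Q1 records employment at every WPAI-MS assessment.

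**Working it through.** **Inputs.** The score formulas are those of SAP 16.3. The plan gives no numerical result, sample size or test for WPAI-MS, so there is no figure to reproduce. All shares and means below are assumptions.

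**Step 1: an ordinary case.** Q2=8, Q4=32, Q5=3: A = 8/40 = 0.20, and score 3 = 0.20 + 0.80 × 0.3 = 0.44. The formula works as intended.

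**Step 2: off work all week because of MS.** Q2=40, Q4=0: A = 40/40 = 1, and score 3 = 1 + (1 − 1) × Q5/10 = 1 for every Q5 from 0 to 10. The score is 100% without knowing Q5. Assigning it is arithmetic and not imputation. With Q5 blank:

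| Score | Result |
|---|---|
| 1 Absenteeism | 100%, kept |
| 2 Presenteeism | none; does not apply |
| 3 Overall impairment | missing, although determined |
| 4 Activity impairment | Q6/10, kept |

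**Step 3: effect on a visit mean of score 3.** Assume 40 employed respondents, with those not off all week averaging 20%.

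- 1 off all week: (39×20 + 1×100)/40 = 22%
- 2 off all week: (38×20 + 2×100)/40 = 24%
- 4 off all week: (36×20 + 4×100)/40 = 28%

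If all of them leave Q5 blank, the reported mean is 20% each time. In general, with a share f off all week and mean m in the others, the understatement is f × (1 − m):

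| m | f=2% | f=5% | f=10% | f=15% |
|---|---|---|---|---|
| 20% | 1.6 | 4.0 | 8.0 | 12.0 |
| 30% | 1.4 | 3.5 | 7.0 | 10.5 |
| 40% | 1.2 | 3.0 | 6.0 | 9.0 |

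Entries are percentage points. The direction is always downward, unless the others are also all at 100%.

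**Step 4: effect on change from baseline.** Let f0 be the share off all week at baseline only and f1 the share off all week at Month 24 only. Everyone else is at 30% at baseline and 25% at Month 24. Patients in f0 and f1 have no change score, so the reported change is −5.0 points. The true change is (1 − f0 − f1)×(−5) + f0×(25 − 100) + f1×(100 − 30).

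| f0 | f1 | True change | Reported −5.0 looks |
|---|---|---|---|
| 2% | 10% | −4.4 − 1.5 + 7.0 = +1.1 | too good |
| 5% | 5% | −4.5 − 3.75 + 3.5 = −4.75 | about right |
| 10% | 2% | −4.4 − 7.5 + 1.4 = −10.5 | too bad |

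**Step 5: not employed.** With Q1=No there is no work time to report. If Q2+Q4=0, A is 0/0 and undefined. The same happens to an employed patient on leave all week for a reason other than MS, which Q3 anticipates. If 10% had stopped work because of MS and were scored 100%, a mean of 30% among workers would become 0.10×100 + 0.90×30 = 37%. If they stopped for other reasons, no such correction applies. Q1 does not say which.

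**The case against.** The strongest reply has four parts.

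- **The ePRO may prevent the problem.** Protocol 9.4 says that patients enter PROs directly in a validated electronic system. If it forces an answer to Q5, score 3 is computed correctly. The documents do not say whether it forces, skips or fills Q5. This stands: the frequency is unknown.
- **The SAP does not forbid 100%.** Filling in an algebraically fixed value is not imputation, and the analysis code for this score is not shown. That is true, but nothing tells the programmer to do it. The same section shows that such a rule can be written: for TSQM, the side-effects score is set to 100 when the patient reports no side effects and the follow-up items do not apply.
- **Restricting scores 1 to 3 to workers is defensible.** It is, provided that the restriction is stated and the employed number is shown. Missing counts by time point show that the number shrinks, but not why.
- **Employment shifts are not a planned endpoint.** Correct. The table is requested so that the change scores can be read, not as a new outcome.

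A reader might go further and infer that the most impaired patients drop out of WPAI-MS altogether, or that the plan makes improvement over time look too large. The documents support neither. Absenteeism and activity impairment survive for the patient off all week, and activity impairment survives for the patient not employed. Baseline ceiling values are lost as well as later ones. Entry requires suboptimal response to an injectable drug (Protocol 9.2.1), so such patients could cluster at baseline, and improvement would then be understated.

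**Conclusion.** The point holds in a limited form. Where Q2>0, Q4=0 and Q5 is blank, SAP 16.3 as written yields no overall work impairment score for a value that its own formula fixes at 100%. The visit mean of that score is then too low: by 1.2 to 12 points for assumed shares of 2–15% and assumed means of 20–40% in the other patients, if all those affected leave Q5 blank. The direction is certain only for the visit mean of this one score; for change from baseline it can go either way.

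Separately, patients not employed cannot be told apart from non-responders. The direction of any resulting bias is unknown, because Q1 does not record why a patient is not working.

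This concerns a descriptive secondary PRO. The primary annualized relapse rate analysis is unaffected.

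**What to change.** In SAP 16.3, WPAI-MS:

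1. When Q1=Yes, Q2>0 and Q4=0, set overall work impairment to 100% whether or not Q5 is answered, and treat presenteeism as not applicable.
2. Classify Q1=No, or Q2+Q4=0, as not applicable for the work scores, reported separately from missing. Show the employed number beside scores 1 to 3 at each time point.
3. Tabulate Q1 at baseline and Months 6, 12 and 24, with shifts from baseline, beside the change scores.

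The cost is a few SAP sentences and one extra table from data already collected. The downside is that visit means of overall impairment may look slightly worse.

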#### PDDS

The PDDS is a patient-reported scale to assess the disability status in patients with MS and it focuses mainly on how patients walk. A higher score represents a higher level of disability. Scores on the PDDS range from 0 (normal) to 8 (bedridden): 0 (Normal), 1 (Mild Disability), 2 (Moderate Disability), 3 (Gait Disability), 4 (Early Cane), 5 (Late Cane), 6 (Bilateral Support), 7 (Wheelchair/Scooter) and 8 (Bedridden).

This single item will be summarized descriptively as a continuous variable using the raw scores.

No imputation will be performed if any values in the PDDS are missing.

## **16.4** Treatment Adherence

Analysis (Analysis Population)	Derivation	Statistical Analysis Methods	Missing data handling
secondary En	dpoint: Treatment adherence		
Secondary (FAS)	Treatment adherence based on modified versions of the MS-TAQ. Data collected at baseline and at Months 1, 2, 13 and 14	Baseline scores over time will be summarized descriptively	See description in Section 16.4

FAS: Full Analysis Set; MS-TAQ: Multiple Sclerosis Treatment Adherence Questionnaire

#### **Treatment adherence questions**

Seven treatment adherence questions, based on modified versions of the MS-TAQ, were developed to determine level of adherence as well as identify barriers to adherence for MS patients taking DMDs. A Self-Injectables Version of the MS-TAQ has been proposed to assess adherence to last previous injectable DMD treatment at Baseline. Another version of the MS-TAQ has been modified for cladribine tablets to assess adherence to cladribine tablets throughout the study.

For both versions the single questions will be summarized descriptively. Items on an ordinal scale will be summarized as continuous variables. No imputation will be performed if any values in the MS-TAQ are missing.

The modified versions of the MS-TAQ are reported in the Appendices.

## 17 References

No references.

## 18 Appendices

#### **TSQM** items

1. How satisfied or dissatisfied are you with the ability of the medication to prevent or treat your condition? (Score 1 to 7)

2. How satisfied or dissatisfied are you with the way the medication relieves your symptoms? (Score 1 to 7)

3. How satisfied or dissatisfied are you with the amount of time it takes the medication to start working? (Score 1 to 7)

4. As a result of taking this medication, do you currently experience any side effects at all? (Score 0[No] or 1[Yes])

5. How bothersome are the side effects of the medication you take to treat your condition?

(Score 1 to 5)

6. To what extent do the side effects interfere with your physical health and ability to function (i.e., strength, energy level, etc.)?

(Score 1 to 5)

7. To what extent do the side effects interfere with your mental function (i.e., ability to think clearly, stay awake, etc.)?

(Score 1 to 5)

8. To what degree have medication side effects affected your overall satisfaction with the medication? (Score 1 to 5)

9. How easy of difficult is it to use the medication in its current form?

(Score 1 to 7)

10. How easy or difficult is it to plan when you will use the medication each time?

(Score 1 to 7)

11. How convenient or inconvenient is it to take the medication as instructed?

(Score 1 to 7)

12. Overall, how confident are you that taking this medication is a good thing for you? (Score 1 to 5)

13. How certain are you that the good things about your medication outweigh the bad things? (Score 1 to 5)

14. Taking all things into account, how satisfied or dissatisfied are you with this medication? (Score 1 to 7)

### HEALTH STATUS QUESTIONNAIRE (SF-36)

This survey asks for your views about your health. This information will help keep track of how you feel and how well you are able to do your usual activities. Thank you for completing this survey!

Item Name	Question Text	Answer Text 1	Answer Text 2	Answer Text 3	Answer Text 4	Answer Text 5	Answer Text 6
	Your Health and Well-Being						
	• This survey asks for your views about your health. This information will help keep track of how you feel and how well you are able to do your usual activities. Thank you for completing this survey!						
	For each of the following questions, please select the one response that best describes your answer.						
SF36v2_GH1	In general, would you say your health is:	Excellent	Very good	Good	Fair	Poor	
SF36v2_HT	Compared to one year ago , how would you rate your health in general now ?	Much better now than one year ago	Somewhat better now than one year ago	About the same as one year ago	Somewhat worse now than one year ago	Much worse now than one year ago	
	The following questions are about activities you might do during a typical day. Does your health now limit you in these activities? If so, how much?						
SF36v2_PF01	Does your health now limit you in vigorous activities , such as running, lifting heavy objects, participating in strenuous sports? If so, how much?	Yes, limited a lot	Yes, limited a little	No, not limited at all			
SF36v2_PF02	Does your health now limit you in moderate activities , such as moving a table, pushing a vacuum cleaner, bowling, or playing golf? If so, how much?	Yes, limited a lot	Yes, limited a little	No, not limited at all			
SF36v2_PF03	Does your health now limit you in lifting or carrying groceries? If so, how much?	Yes, limited a lot	Yes, limited a little	No, not limited at all			
SF36v2_PF04	Does your health now limit you in climbing several flights of stairs? If so, how much?	Yes, limited a lot	Yes, limited a little	No, not limited at all			
SF36v2_PF05	Does your health now limit you in climbing one flight of stairs? If so, how much?	Yes, limited a lot	Yes, limited a little	No, not limited at all			
SF36v2_PF06	Does your health now limit you in bending, kneeling, or stooping? If so, how much?	Yes, limited a lot	Yes, limited a little	No, not limited at all			
SF36v2_PF07	Does your health now limit you in walking more than a mile ? If so, how much?	Yes, limited a lot	Yes, limited a little	No, not limited at all			
SF36v2_PF08	Does your health now limit you in walking several hundred yards ? If so, how much?	Yes, limited a lot	Yes, limited a little	No, not limited at all			
SF36v2_PF09	Does your health now limit you in walking one hundred yards ? If so, how much?	Yes, limited a lot	Yes, limited a little	No, not limited at all			
SF36v2_PF10	Does your health now limit you in bathing or dressing yourself? If so, how much?	Yes, limited a lot	Yes, limited a little	No, not limited at all			

For each of the following questions, please select the one response that best describes your answer.

Item Name	Question Text	Answer Text 1	Answer Text 2	Answer Text 3	Answer Text 4	Answer Text 5	Answer Text 6
	During the past 4 weeks , how much of the time have you had any of the following problems with your work or other regular daily activities as a result of your physical health?						
SF36v2_RP1	During the past 4 weeks , how much of the time have you cut down on the amount of time you spent on work or other activities as a result of your physical health?	All of the time	Most of the time	Some of the time	A little of the time	None of the time	
SF36v2_RP2	During the past 4 weeks , how much of the time have you accomplished less than you would like as a result of your physical health ?	All of the time	Most of the time	Some of the time	A little of the time	None of the time	
SF36v2_RP3	During the past 4 weeks , how much of the time were you limited in the kind of work or other activities as a result of your physical health ?	All of the time	Most of the time	Some of the time	A little of the time	None of the time	
SF36v2_RP4	During the past 4 weeks , how much of the time have you had difficulty performing the work or other activities as a result of your physical health (for example, it took extra effort)?	All of the time	Most of the time	Some of the time	A little of the time	None of the time	
	During the past 4 weeks , how much of the time have you had any of the following problems with your work or other regular daily activities as a result of any emotional problems (such as feeling depressed or anxious)?						
SF36v2_RE1	During the past 4 weeks , how much of the time have you cut down on the amount of time you spent on work or other activities as a result of any emotional problems (such as feeling depressed or anxious)?	All of the time	Most of the time	Some of the time	A little of the time	None of the time	
SF36v2_RE2	During the past 4 weeks , how much of the time have you accomplished less than you would like as a result of any emotional problems (such as feeling depressed or anxious)?	All of the time	Most of the time	Some of the time	A little of the time	None of the time	
SF36v2_RE3	During the past 4 weeks , how much of the time have you done work or other activities less carefully than usual as a result of any emotional problems (such as feeling depressed or anxious)?	All of the time	Most of the time	Some of the time	A little of the time	None of the time	
SF36v2_SF1	During the past 4 weeks , to what extent has your physical health or emotional problems interfered with your normal social activities with family, friends, neighbors, or groups?	Not at all	Slightly	Moderately	Quite a bit	Extremely	
SF36v2_BP1	How much bodily pain have you had during the past 4 weeks ?	None	Very mild	Mild	Moderate	Severe	Very severe
SF36v2_BP2	During the past 4 weeks , how much did pain interfere with your normal work (including both work outside the home and housework)?	Not at all	A little bit	Moderately	Quite a bit	Extremely	
	These questions are about how you feel and how things have been with you during the past 4 weeks . For each question, please give the one answer that comes closest to the way you have been feeling.						

Item Name	Question Text	Answer Text 1	Answer Text 2	Answer Text 3	Answer Text 4	Answer Text 5	Answer Text 6
SF36v2_VT1	How much of the time during the past 4 weeks did you feel full of life?	All of the time	Most of the time	Some of the time	A little of the time	None of the time	
SF36v2_MH1	How much of the time during the past 4 weeks have you been very nervous?	All of the time	Most of the time	Some of the time	A little of the time	None of the time	
SF36v2_MH2	How much of the time during the past 4 weeks have you felt so down in the dumps that nothing could cheer you up?	All of the time	Most of the time	Some of the time	A little of the time	None of the time	
SF36v2_MH3	How much of the time during the past 4 weeks have you felt calm and peaceful?	All of the time	Most of the time	Some of the time	A little of the time	None of the time	
SF36v2_VT2	How much of the time during the past 4 weeks did you have a lot of energy?	All of the time	Most of the time	Some of the time	A little of the time	None of the time	
SF36v2_MH4	How much of the time during the past 4 weeks have you felt downhearted and depressed?	All of the time	Most of the time	Some of the time	A little of the time	None of the time	
SF36v2_VT3	How much of the time during the past 4 weeks did you feel worn out?	All of the time	Most of the time	Some of the time	A little of the time	None of the time	
SF36v2_MH5	How much of the time during the past 4 weeks have you been happy?	All of the time	Most of the time	Some of the time	A little of the time	None of the time	
SF36v2_VT4	How much of the time during the past 4 weeks did you feel tired?	All of the time	Most of the time	Some of the time	A little of the time	None of the time	
SF36v2_SF2	During the past 4 weeks , how much of the time has your physical health or emotional problems interfered with your social activities (like visiting with friends, relatives, etc.)?	All of the time	Most of the time	Some of the time	A little of the time	None of the time	
	How TRUE or FALSE is each of the following statements for you?						
SF36v2_GH2	I seem to get sick a little easier than other people.	Definitely true	Mostly true	Don't know	Mostly false	Definitely false	
SF36v2_GH3	I am as healthy as anybody I know.	Definitely true	Mostly true	Don't know	Mostly false	Definitely false	
SF36v2_GH4	I expect my health to get worse.	Definitely true	Mostly true	Don't know	Mostly false	Definitely false	
SF36v2_GH5	My health is excellent.	Definitely true	Mostly true	Don't know	Mostly false	Definitely false	
	SF-36v2 ® Health Survey © 1992, 2000, 2009 Medical Outcomes Trust and QualityMetric Incorporated. All rights reserved. SF-36 ® is a registered trademark of Medical Outcomes Trust. (SF-36v2 ® Health Survey Standard, United States (English))						

